### Overall Survival (OS)

Overall survival (OS) is defined as the time from the Treatment start date to the date of death due to any cause. Patients without the event will be censored at the Last contact date.

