### *6.7.2. Overall Survival*

Overall survival (OS) will be monitored from the time of patient enrollment until the patient is lost to follow-up, deceased, the study is considered complete, or a maximum of 1 year is reached. The patient's medical record will be consulted approximately every 3 months to assess survival.

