## **APPENDICES**

**Appendix 1. Schedule of Events (Phase II)**

Day	Screening a		Cycle 1				Cycle 2			Cycles ≥3 s		Discontinuation t	30-Day Follow-up v	Q 3 Months Follow-up
	≤28		1 b	2	8	15	1	8	15	1	15			
	V1	V2												
Informed consent	X													
Enrollment c	X		X											
Demographics d	X													
Medical and oncology history e	X													
Weight and height f	X		X				X			X		X		
Pregnancy test g	X		X				X			X		X		
FSH and estradiol h	X													
Tumor biopsy i		X						X						
Blood sample for molecular profile			X				X			X		X		
Physical exam j	X		X		X	X	X	X	X	X	X	X	X	
Vital Signs k	X		X		X	X	X	X	X	X	X	X	X	
12-Lead ECG l	X		X			X	X		X	X	X	X		
ECOG performance status m	X		X				X			X		X	X	
Hematology n	X		X		X	X	X	X	X	X	X	X	X	
Clinical chemistry o	X		X		X	X	X	X	X	X	X	X	X	
Urinalysis	X		X				X			X		X		
Concomitant medication review	X		X		X	X	X			X		X	X	
AK-01 dosing p			X				X			X				
PK sampling q			X	X	X	X						X		
AK-01 compliance					X	X	X			X		X		
AE monitoring	X	X	X	X	X	X	X	X	X	X	X	X	X	
Radiographic tumor assessment	X									X r		X u		
Survival assessment														X w

Abbreviations: AE – adverse event; CT – computed tomography; C – cycle; ECG – electrocardiogram; ECOG – Eastern Cooperative Oncology Group; EDC – electronic data capture; D – day; FSH – follicle stimulating hormone; hr – hour; ICD – informed consent documents; MRI – magnetic resonance imaging; PK – pharmacokinetic; RECIST – Response Evaluable Criteria in Solid Tumors; V – visit; Q 3 months – every 3 months

- a. All screening procedures must be performed within 28 days prior to Cycle 1 Day 1 (C1D1). Patients will undergo preliminary screening procedures at Visit 1 (V1) before becoming eligible for pre-treatment tumor biopsy (V2).

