- v. Patients will attend a follow-up visit 30 days (+/- 7 days) following the last dose of IMP.
- w. Patient survival will be confirmed approximately every 3 months for up to 1 year.

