## 7.3. General Definitions

**Treatment start date** is defined as the first date when a nonzero dose of AK-01 was administered. It will be derived based on the “AK-01 compliance” eCRF page.

**Treatment end date** is defined as the last date when a nonzero dose of AK-01 was administered. It will be taken from the field “Date of last drug intake” in the “Discontinuation from study treatment” eCRF page.

**Study day** for all assessments will be derived from the Treatment start date. It will be calculated as follows:

- Date of assessment – Treatment start date + 1; for assessments on or after Treatment start date
- Date of assessment – Treatment start date; for assessments before Treatment start date

**Last contact date** will be derived as the latest date of the following:

- Date of any visit
- Date of any other assessment, i.e. date of ECG, ECOG assessment, physical examination or pregnancy test, Date of blood sampling (laboratory tests, molecular profile, PK), date of skin/tumor biopsy, Date of last drug intake, date of discontinuation, start/end date regarding AK-01 compliance, AEs or concomitant medications, date of assessment regarding the response evaluation
- Date of last known alive in the Survival eCRF page

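### Survival monitoring stops at 1 year or study completion, but OS is censored at any later contact, so the Kaplan-Meier tail rests mainly on patients still on AK-01

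*SAP*

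**What the plan says.** Protocol 6.7.2 starts survival monitoring at enrollment and continues it "until the patient is lost to follow-up, deceased, the study is considered complete, or a maximum of 1 year is reached". Appendix 1 footnote w says "Patient survival will be confirmed approximately every 3 months for up to 1 year" but does not say when that year begins. The schedule marks the survival check only in the column headed "Q 3 Months Follow-up", which comes after the Discontinuation and 30-day visits.

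SAP 6.1 measures OS from the Treatment start date to death from any cause. For everyone else, "Patients without the event will be censored at the Last contact date". SAP 7.3 says this date "will be derived as the latest date of the following", and the list opens with "Date of any visit". It goes on to assessments, blood samples, drug intake, adverse-event and concomitant-medication dates, and the date last known alive on the survival page. SAP 7.1 applies no analysis cut-off.

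Protocol 3.2 lets dosing continue until progression. Protocol 3.7 keeps assessments going for patients who continue past 8 cycles. Protocol 8.2 censors OS at last contact for patients alive at study completion or lost to follow-up, and gives no rule for patients alive when the 1-year limit is reached.

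SAP 9.6.2 plans a Kaplan-Meier curve for OS, with median and quartiles and 95% confidence intervals. SAP 6.3 lists OS as exploratory in Phase II.

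**The concern.** Kaplan-Meier estimation assumes that patients who leave the risk set have the same outlook as those who stay. Here, beyond the end of survival monitoring, staying depends on treatment status. A patient on AK-01 still has visits, scans and dosing records, so OS time and deaths continue to accrue. A patient who has stopped drug is no longer checked. Dosing continues only without progression and with benefit in the investigator's opinion, so treatment status is tied to prognosis.

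The part of the curve beyond the horizon, and any quantile that falls in it, would then describe mainly patients still on treatment while being labelled as survival of the whole cohort. In a single-arm trial, OS can only be read against outside figures, so a distorted tail has no internal comparator to expose it.

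**Working it through.** The documents give no assumed survival rate, median or event count, so there is no planned figure to reproduce. Every rate below is an assumption.

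**Step 1. Who can still be observed after the horizon?**

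| Source of contact dates | On AK-01 | Off AK-01 |
|---|---|---|
| Visits, labs, scans, dosing (SAP 7.3; Protocol 3.2, 3.7) | Continue to progression, no time limit | Discontinuation and 30-day visits only |
| Survival check (Protocol 6.7.2) | Ends at 1 year or study completion | Ends at 1 year or study completion |
| Drug-related AE follow-up (Protocol 6.5.4) | Yes | Until resolution, death, loss to follow-up or new treatment |

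On the wording of 6.7.2, the late risk set is mainly, though not exclusively, patients on drug.

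**Step 2. Hand calculation, year counted from enrollment.** Assume 50% are alive at month 12, a fraction f of these are on drug, and monthly death hazards are 0.03 on drug and 0.08 off drug, with no switching between months 12 and 18.

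- True S(18) = 0.5 × [(1 − f) × exp(−0.08 × 6) + f × exp(−0.03 × 6)]
- Kaplan-Meier under the plan, if only on-drug patients remain at risk = 0.5 × exp(−0.03 × 6) = 0.418

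| f | True S(18) | Plan | Excess |
|---|---|---|---|
| 0.1 | 0.320 | 0.418 | 0.098 |
| 0.2 (base case) | 0.331 | 0.418 | 0.087 |
| 0.3 | 0.342 | 0.418 | 0.076 |

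The plan's figure does not move with f; it is set by the on-drug hazard alone. In the base case 30 × 0.5 × 0.2 = 3 patients of a full cohort of 30 carry the tail.

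**Step 3. Simulation with discontinuation over time.** There were 400,000 patients per scenario, with exponential time to discontinuation, exponential survival after it, and an on-drug death hazard of 0.01 per month. Reading A counts 12 months from enrollment, with later contact only while on drug plus 30 days. Reading B counts 12 months from discontinuation. Scenarios are labelled by median months to discontinuation / median months of survival after it.

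| Scenario | True S(18) | Reading A | Reading B | True median | Median, A |
|---|---|---|---|---|---|
| 3/6 | 0.219 | 0.343 | 0.224 | 10.1 | 10.1 |
| 4/9 | 0.384 | 0.511 | 0.391 | 14.2 | 19.1 |
| 6/9 | 0.452 | 0.576 | 0.464 | 16.3 | 26.3 |
| 6/12 | 0.530 | 0.637 | 0.541 | 19.2 | 33.9 |

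The 18-month excess is 0.11 to 0.13 under reading A and about 0.01 or less under reading B. Under B it reaches about 0.03 at 24 months (0.336 against 0.308 in the 6/9 scenario). In the 3/6 scenario the median is unaffected, but the time at which survival falls to 25% moves from 16.8 to 27.6 months under A. Under both readings the estimate at month 12 equals the true value.

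**Step 4. Control.** With equal hazards on and off drug (4/9 scenario, reading A), S(18) is 0.251 against a true 0.249. The bias comes from the hazard difference.

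**Step 5. The study-completion stop.** Under Protocol 3.7 the study is complete once every Phase II patient has had at least 8 cycles, progressed or discontinued. Eight cycles are 8 × 21 = 168 days, or 24 weeks. If completion falls 24 weeks after the last patient starts, anyone enrolled less than about 52 − 24 = 28 weeks before that patient loses survival monitoring before a full year. Patients continuing on drug are still assessed, so the same asymmetry can begin before month 12.

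**The case against.** A reader might infer more than the documents support, in four ways.

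- **That only patients on drug remain at risk.** The 30-day visit and follow-up of drug-related adverse events also produce later contact dates. The risk set is mainly on-drug, not wholly so.
- **That the tail is biased upward as a matter of fact.** This needs a lower death hazard on drug and no capture of late off-drug deaths. The first is plausible. The second is not settled: SAP 6.1 counts death from any cause and has no rule for deaths learned of after monitoring ends. Counting those while unfollowed survivors stay censored would pull the curve down.
- **That the start of the year hardly matters.** Protocol 6.7.2 is the only place that states a start, and it says enrollment. The schedule layout and footnote w leave discontinuation open, and on that reading the 18-month bias falls roughly tenfold.
- **That nothing before month 12 is affected.** That is true of the 1-year limit, but not of the study-completion stop.

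It can also fairly be said that OS is exploratory, that Protocol 8.1.6 says only that it may be summarized, that no landmark beyond 12 months is planned, and that cohorts of at most 30 give wide intervals. SAP censoring at last contact agrees with Protocol 8.2. These points limit the importance of the problem. They do not remove it, because neither document gives a common horizon.

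**Conclusion.** The point holds in limited form. On the wording of Protocol 6.7.2, OS follow-up past 1 year or study completion depends on treatment status, so the Kaplan-Meier tail and any quantile in it are subject to informative censoring.

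If the year runs from enrollment, 18-month OS is overstated by about 0.09 (hand-calculation base case) to 0.13 (simulation), and by 0.08 in the mildest variation shown. If it runs from discontinuation, the overstatement is about 0.01. These sizes rest wholly on assumed hazards and discontinuation rates, and on late off-drug deaths not being recorded. The upward direction is probable, not established. The primary ORR analysis is untouched. This is an inexpensive improvement to an exploratory analysis.

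**What to change.** First, reconcile Protocol 6.7.2 with Appendix 1 footnote w on when the survival year starts.

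If it starts at enrollment, add to SAP 6.1:

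*OS is censored at the earliest of Last contact date, the end of the 1-year survival follow-up (365 days after enrollment) and the study completion date; deaths after that horizon are listed but not counted as events, whatever the treatment status.*

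Report OS quantiles only if they are reached within the horizon, and show numbers at risk under each curve.

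Any landmark should be on the treatment-start clock at a time all patients could reach. OS starts at first dose, whereas enrollment falls between the end of screening and first dose, and screening lies within 28 days before first dose (Appendix 1 footnotes a and c). Under the 1-year limit alone, the latest day sure to be reachable is therefore 365 − 28 = 337. The study-completion stop may require an earlier one.

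If the year is meant to start at discontinuation, do not use the enrollment cap, because it would discard legitimate off-drug follow-up. State the start and one rule for later deaths instead.

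The cost is SAP wording, a line of code, and the loss of post-horizon follow-up for the few patients still on drug. The alternative is to follow every patient for survival on the same schedule regardless of treatment status. That keeps the tail but needs a protocol change and more work at the sites.

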## 6.2. Phase I

The following endpoints were defined for Phase I

#### Primary

- DLTs

#### Secondary

- Safety: type, frequency and severity of AEs, laboratory parameters

#### Exploratory

- PK parameters

- PD parameters (hematology)
- PD markers of AK-01 target engagement in skin biopsies
- ORR, DOR, BOR, DCR, PFS, OS

## 6.3. Phase II

The following endpoints were defined for Phase II

Primary

- ORR

Secondary

- Safety and tolerability: type, frequency and severity of AEs, laboratory parameters
- PK and PD parameters

Exploratory

- DOR, BOR, DCR, PFS, OS
- ORR and other clinical endpoints (BOR, OS, PFS) vs molecular profiles

## 7. Definitions

### 7.1. Study Database

Data collected and validated in the clinical study database will be analyzed. No analysis cut-off date will be applied.

### 7.2. Labels and Tags Used in SAP and/or Outputs

For indication of cohorts, the following labels will be used in the outputs:

- Phase I, where cohorts are defined by the dose assigned: AK-01 25mg BID, AK-01 50mg BID, AK-01 75mg BID, etc.
- Phase II, where cohorts are defined by the tumor type: BC, SCLC, etc. (based on the indications selected)

For indications of time-points, the notation will include cycle and day numbers, e.g. “Cycle 2 Day 8” or “C2D8”.

## 7.3. General Definitions

**Treatment start date** is defined as the first date when a nonzero dose of AK-01 was administered. It will be derived based on the “AK-01 compliance” eCRF page.

**Treatment end date** is defined as the last date when a nonzero dose of AK-01 was administered. It will be taken from the field “Date of last drug intake” in the “Discontinuation from study treatment” eCRF page.

**Study day** for all assessments will be derived from the Treatment start date. It will be calculated as follows:

- Date of assessment – Treatment start date + 1; for assessments on or after Treatment start date
- Date of assessment – Treatment start date; for assessments before Treatment start date

**Last contact date** will be derived as the latest date of the following:

- Date of any visit
- Date of any other assessment, i.e. date of ECG, ECOG assessment, physical examination or pregnancy test, Date of blood sampling (laboratory tests, molecular profile, PK), date of skin/tumor biopsy, Date of last drug intake, date of discontinuation, start/end date regarding AK-01 compliance, AEs or concomitant medications, date of assessment regarding the response evaluation
- Date of last known alive in the Survival eCRF page

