## 4.2. Discontinuation

### 4.2.1. Discontinuation of Patients

In accordance with the guidelines of the International Conference on Harmonisation (ICH) Good Clinical Practices (GCP), Health Canada, European Medicines Agency, and United States Food and Drug Administration, a patient may withdraw their participation in this study at any time.

Criteria to discontinue patients from study treatment will include but will not be limited to:

- Objective disease progression based on RECIST v. 1.1 as determined by the investigator
- Unacceptable toxicity
- Significant protocol violation
- Global deterioration of health status
- Lost to follow-up
- Refusal of further treatment by patient
- Study termination by sponsor
- Dosing is delayed by more than 21 days due to toxicity

Reasons for discontinuation from the study may include:

- Study termination by sponsor
- Lost to follow-up
- Withdrawal of consent

If a patient is found to not meet the enrollment criteria but was inadvertently enrolled, the patient must be discontinued from the study and the sponsor or its designee must be informed. An exception to this requirement may be granted in rare circumstances where the patient has a serious or life threatening condition for which there is no effective alternative therapy and, in the opinion of the investigator, is receiving benefit from study treatment. In this case, the investigator must obtain documented approval from the sponsor's medical representative to allow the patient to continue receiving IMP.

Following discontinuation or withdrawal, the investigator will request that the patient return all unused IMP and packaging, and participate in the Discontinuation and 30-Day Follow-up visits. If it is in the best interest of the patient to start a new anti-cancer treatment prior to this date, the follow-up assessments may be performed sooner, so long as they are completed prior to initiation of the new therapy.

The primary reason for withdrawal, patient outcome, and the date of withdrawal will be documented. Every effort will be made to adequately follow the patient for any unresolved AEs. In the case of withdrawal due to global deterioration of health status, the signs, symptoms, or results that motivated this decision will be documented.

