### **8.2. Missing Data**

In general, data imputation to accommodate missing data will not be performed. Patients who are not evaluable for PFS and OS will be considered censored at time zero. PFS will be censored at the time of last tumor assessment for patients lost to follow-up or who do not experience disease progression or death during the study. OS will be censored at the time of last contact for patients who are alive at study completion or who are lost to follow-up. For safety data, if the causality of an AE is unknown, it will be assumed there was a reasonable possibility the event was related to IMP.

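### The Last contact date that censors OS counts the discontinuation date whatever the reason, so a lost patient can be censored after last being known alive

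*SAP*

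**What the plan says.** For OS, SAP 6.1 states: "Patients without the event will be censored at the Last contact date". SAP 7.3 defines that date. It "will be derived as the latest date of the following", and three groups of dates follow:

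- "Date of any visit", with no condition that the patient was seen;
- the date of any other assessment, a long item that ends with tumor response dates and includes "Date of last drug intake, date of discontinuation, start/end date regarding AK-01 compliance, AEs or concomitant medications";
- "Date of last known alive in the Survival eCRF page".

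Protocol 4.2.1 has a list headed "Reasons for discontinuation from the study may include". Its three entries are termination by the sponsor, loss to follow-up and withdrawal of consent. Note t to the schedule of events (Protocol Appendix 1) has the discontinuation date recorded with its reason, but does not say which date applies to a patient who cannot be reached.

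On survival follow-up, Protocol 6.7.2 says the patient's "medical record will be consulted approximately every 3 months to assess survival", for at most 1 year. Protocol 8.2 says "OS will be censored at the time of last contact for patients who are alive at study completion or who are lost to follow-up" and does not define last contact.

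**The concern.** An OS censoring date should be the last day on which the patient is documented alive. Kaplan-Meier treats every day before it as a day on which a death would have been seen. A site can declare a patient lost only after contact has failed, so the declaration can come later than the last evidence of life. A sponsor's decision to terminate need not coincide with any contact either.

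SAP 7.3 does collect the right variable, the last-known-alive date. Because the latest date wins, a later administrative date replaces it. The patient then stays in the risk set for time in which no death could be observed. The error runs in one direction: it lowers the estimated hazard and raises the curve. It is separate from the 1-year limit on follow-up, since it acts before that limit.

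What is at stake is the set of OS curves, medians and quartiles that SAP 9.6.2 reports with 95% confidence intervals. Those intervals reflect sampling error only and do not cover a bias built into the censoring rule.

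**Working it through.** **Figure to reproduce.** None. The documents state no OS median, survival rate or loss rate, so only direction and size can be examined.

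**Inputs from the documents.** Censoring at the latest listed date (SAP 6.1 and 7.3); follow-up of at most 12 months (Protocol 6.7.2); Kaplan-Meier by Phase II cohort (SAP 9.6.2); up to 30 patients per cohort (SAP 5.1.2).

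**Assumptions, not in the documents.** Exponential survival with median m of 6, 9 or 12 months. Annual probability p of being lost, in the absence of death, of 5%, 10% or 20%; because deaths come first for many patients, the share actually lost is 2.8% to 14.5%. Every lost patient is recorded d months after last being known alive, with d = 1 or 3 (3 months is one record-review interval). d = 0 is the correct date.

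**Direction.** With death hazard λ = ln 2 / m and loss hazard γ = −ln(1 − p)/12 per month, late censoring keeps roughly γd extra patients in the risk set for each patient truly under observation. None of these extra patients can contribute a death. The estimated hazard is therefore about λ/(1 + γd), which is below λ whenever γ and d are positive.

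**One case by hand (m = 6, p = 20%, d = 3).**
- λ = 0.6931/6 = 0.1155 and γ = 0.2231/12 = 0.0186.
- Estimated hazard = 0.1155/(1 + 0.0558) = 0.1094.
- 12-month survival = exp(−12 × 0.1094) = 0.269, against a true 0.250. The excess is about 1.9 points.

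**Simulation.** 400,000 patients per scenario, Kaplan-Meier survival at 12 months:

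| Median (months) | Annual loss | Share lost | d = 0 | d = 1 | d = 3 |
|---|---|---|---|---|---|
| 6 | 5% | 2.8% | 0.250 | 0.252 | 0.255 |
| 6 | 10% | 5.6% | 0.250 | 0.253 | 0.260 |
| 6 | 20% | 11.1% | 0.250 | 0.257 | 0.270 |
| 9 | 5% | 3.3% | 0.399 | 0.400 | 0.403 |
| 9 | 10% | 6.6% | 0.398 | 0.401 | 0.408 |
| 9 | 20% | 13.2% | 0.396 | 0.402 | 0.415 |
| 12 | 5% | 3.6% | 0.500 | 0.502 | 0.504 |
| 12 | 10% | 7.3% | 0.500 | 0.503 | 0.509 |
| 12 | 20% | 14.5% | 0.499 | 0.505 | 0.517 |

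The true values are 0.250, 0.397 and 0.500, so d = 0 recovers them to within simulation error. Measured against d = 0, the overstatement at 12 months runs from about 0.2 point (5% loss, 1 month) to 2.0 points (20% loss, 3 months, median 6). The 0.1 point shown for median 9 with 5% loss and 1 month is rounding: the formula gives γ = 0.0513/12 = 0.0043 and survival of 0.3984 against 0.3969, or about 0.15 point.

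At 6 months the overstatement is 0.1 to 1.6 points. The median moves from 5.987 to 6.014 at the small end (0.03 month) and from 8.975 to 9.453 at the large end (0.48 month).

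**Against sampling error.** For 30 patients and 50% survival, the 95% half-width is 1.96 × √(0.25/30) = 0.179, or about 18 points.

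**The case against.** The strongest reply is that the plan does not say a wrong date will be entered. If sites enter the true last contact as the discontinuation date, or if nobody is lost, nothing goes wrong. That stands, so the conclusion is that OS can be overstated, not that it is.

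Date of discontinuation may also mean stopping treatment, since the eCRF page that SAP 7.3 names elsewhere is the treatment-discontinuation page. Patients on treatment are seen at least on Days 1 and 15 of each cycle, so the gap would be short and the bias at or below the low end. This reading is possible but not settled. SAP 9.4 also reports study discontinuation with reasons, and loss to follow-up and sponsor termination appear in both lists in Protocol 4.2.1.

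A reader might go further in four ways that the documents do not support:

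- **That the quoted line is generally unsound.** Dosing dates, and the ECG, examination, blood-sampling and biopsy dates in the same item, require a living patient. Adverse-event and medication dates normally rest on contact.
- **That record reviews already act as visit dates.** The protocol says records are consulted about every 3 months. Nothing says the consultation date is stored as a visit, and survival follow-up has its own eCRF page. This is a case to close off, not an established fault.
- **That a withdrawal-of-consent date is equally suspect.** A patient who withdraws is alive that day. Dropping the date would discard valid follow-up.
- **That the SAP contradicts Protocol 8.2.** The protocol leaves last contact undefined and SAP 7.3 supplies a definition. The definition is too broad for lost patients, but it does not conflict with any stated rule.

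Finally, OS is exploratory, single-arm and untested (SAP 6.3), and the bias is small beside sampling error. That limits the importance of the point; it does not make the rule right.

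**Conclusion.** The point holds as a minor defect in a stated derivation rule. As written, SAP 7.3 lets a discontinuation date recorded for loss to follow-up, or for sponsor termination without contact, displace the date the patient was last known alive. Any resulting bias in OS is upward and can occur within the first year.

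The sizes in the working rest entirely on the assumed loss rates, gaps and exponential survival. They also give every lost patient the full delay, so they lean towards the worst case for those inputs. Patients with a recorded death are unaffected, as are the primary ORR test and its power.

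**What to change.** Add to SAP 7.3 a censoring date specific to OS: the last date on which the patient is documented alive, taken from attended visits or assessments, dosing, a withdrawal of consent made by the patient, or the last-known-alive field. State two exclusions:

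- The discontinuation date is not used when the reason is loss to follow-up or sponsor termination without patient contact. If the patient was in fact seen, the visit's own date still counts.
- If a 3-monthly record consultation is stored as a visit, the last-known-alive date is used in place of the consultation date.

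The cost is a sentence or two in the SAP before database lock. The reason for discontinuation and the last-known-alive date are already collected, so no new data are needed. The only downside is that reported OS may be slightly shorter.
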